8.2.2.1 Initial Tumor Scans

Diagnostic quality anatomic scans (typically contrast enhanced CT scan) and metabolic scans via FDG-PET must be performed during Screening.

[figure not shown]
Initial tumor scans at Screening must be performed within 28 days prior to the date of the first dose of study intervention. Any scans obtained after Cycle 1 Day 1 cannot be included in the screening assessment. The site must review screening scans to confirm the participant has measurable disease as defined in the inclusion criteria.

Disease assessments or scans performed as part of routine clinical management are acceptable for use as the screening scan if they are of diagnostic quality and performed within 28 days prior to the first dose of study intervention.

[figure not shown]
8.2.2.2 Lymphoma Disease Response Assessment/Scan During the Study

After Screening, disease response assessments will occur at Week 12 (± 7 days) and every 12 weeks (± 7 days) thereafter as detailed in the SoA (Section 1.3, [Table 1](#)). The first

[figure not shown]
CCI

[figure not shown]
CCI

[figure not shown]
CCI

[figure not shown]
CCI

[figure not shown]
CCI

[figure not shown]
CCI

[figure not shown]
CCI

[figure not shown]
CCI

[figure not shown]
CCI

[figure not shown]
CCI

[figure not shown]
CCI

[figure not shown]
CCI

[figure not shown]
CCI

CCI

CCI

9 STATISTICAL ANALYSIS PLAN

This section outlines the statistical analysis strategy and procedures for the study. Changes to analyses made after the protocol has been finalized will be documented in a sSAP and referenced in the CSR for the study. Post hoc exploratory analyses will be clearly identified in the CSR.

9.1 Statistical Analysis Plan Summary

Key elements of the statistical analysis plan are summarized below; the comprehensive plan is provided in Sections 9.2 through 9.12.

Study Design Overview	This is a Phase 2 Study of Pembrolizumab (MK-3475) 400 mg Q6W in Participants with rrCHL or rrPMBCL.
Treatment Assignment	Participants meeting inclusion/exclusion criteria will be allocated to one of the 2 cohorts, rrCHL or rrPMBCL, and receive 400 mg of pembrolizumab Q6W. The population of each cohort, rrCHL and rrPMBCL, is defined in Section 3.
Analysis Populations	Efficacy: APaT Safety: APaT
Primary Endpoints	Objective Response per Lugano classification as assessed by Investigator.
Secondary Endpoints	Objective Response per Lugano classification as assessed by BICR. DOR per Lugano classification as assessed by Investigator. DOR per Lugano classification as assessed by BICR. AEs and study intervention discontinuations due to AEs.
Statistical Methods for Key Efficacy Analyses	The point estimate of ORR will be provided together with 95% CI using exact binomial method proposed by Clopper and Pearson (1934) [Clopper, C. J. and Pearson, E. S. 1934].
Statistical Methods for Key Safety Analyses	Summary statistics (counts, percentage, mean, standard deviation, etc.) will be provided for the safety endpoints as appropriate.

Interim Analyses	There are no planned interim analyses for this study.
Multiplicity	No multiplicity adjustment is planned as there is no hypothesis testing.
Sample Size and Power	The sample size is expected to be approximately 60 participants with no required minimum in either cohort.

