1 PROTOCOL SUMMARY

1.1 Synopsis

Protocol Title: A Phase 2 Study of Pembrolizumab (MK-3475) every 6 weeks (Q6W) in Participants with Relapsed or Refractory Classical Hodgkin's Lymphoma (rrcHL) or Relapsed or Refractory Primary Mediastinal Large B-cell Lymphoma (rrPMBCL)

Short Title: Phase 2 study of MK 3475 Q6W in rrcHL or rrPMBCL

Acronym: None

Hypotheses, Objectives, and Endpoints:

Hypotheses are aligned with objectives in the Objectives and Endpoints table.

In male and female, programmed cell death 1 protein (PD-1) naïve, participants ≥ 18 years of age with either

- rrcHL who have failed to respond or relapsed after ≥ 1 line of multiagent therapy (can include brentuximab vedotin), or who have failed to achieve a complete response (CR) or relapsed after auto-stem cell transplantation (SCT), or are ineligible for auto-SCT,

OR

- rrPMBCL who have failed to respond or relapsed after ≥ 2 lines of therapy (at least 1 of the prior lines of therapy must contain a rituximab-based regimen), or who have failed to achieve a CR or relapsed after auto-SCT, or are ineligible for auto-SCT:

Primary Objective	Primary Endpoint
To evaluate objective response rate (ORR), by cohort, rrcHL and rrPMBCL, as assessed by the investigator according to Lugano classification criteria [Cheson, B. D., et al 2014] in individuals treated with pembrolizumab Q6W.	Participants with complete response (CR) or partial response (PR).
Secondary Objectives	Secondary Endpoints
To evaluate objective response rate (ORR), by cohort, rrcHL and rrPMBCL, as assessed by blinded independent central review (BICR) according to Lugano classification criteria [Cheson, B. D., et al 2014] in individuals treated with pembrolizumab Q6W.	Participants with complete response CR or PR.

To evaluate duration of response (DOR), by cohort, rrcHL and rrPMBCL, as assessed by the investigator according to Lugano classification criteria [Cheson, B. D., et al 2014] in individuals treated with pembrolizumab Q6W.	The time from first documented evidence of CR or PR until disease progression or death due to any cause, whichever occurs first.
To evaluate duration of response (DOR), by cohort, rrcHL and rrPMBCL, as assessed by BICR according to Lugano classification criteria [Cheson, B. D., et al 2014] in individuals treated with pembrolizumab Q6W.	The time from first documented evidence of CR or PR until disease progression or death due to any cause, whichever occurs first.

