To evaluate the pharmacokinetic (PK) profile, immunogenicity of pembrolizumab 400 mg Q6W.	-PK parameters of pembrolizumab including AUC, C _{max} and C _{min} . -Antidrug antibody levels.
To evaluate the safety and tolerability of pembrolizumab Q6W.	-Adverse Events (AEs). -Discontinuations due to AEs.

Overall Design:

Study Phase	Phase 2
Primary Purpose	Treatment
Indication	Relapsed and/or Refractory Primary mediastinal large B-cell lymphoma, Hodgkin's lymphoma
Population	PD-1 naïve adult participants with rrcHL, who have failed to respond or relapsed after ≥1 line of multiagent therapy (with or without brentuximab vedotin), or who have failed to achieve a CR or relapsed after auto-SCT, or are ineligible for auto-SCT OR PD-1 naïve adult participants with rrPMBCL who have failed to respond or relapsed after ≥2 lines of therapy, or failed to achieve a CR or relapsed after auto-SCT, or are ineligible for auto-SCT
Study Type	Interventional

Intervention Model	Single Group This is a single group, multi site study.
Type of Control	No Treatment Control
Study Blinding	Unblinded open-label
Blinding Roles	No blinding
Estimated Duration of Study	The Sponsor estimates that the study will require approximately 4 years from the time the first participant (or their legally acceptable representative) provides documented informed consent until the last participant's last study-related contact.

Number of Participants:

Approximately 60 participants will be allocated into 2 cohorts based on baseline disease as described in Section 6.3.1.

Intervention Groups and Duration:

Arm Name	Intervention Name	Unit Dose Strength(s)	Dosage Level(s)	Route of Administration	Regimen/ Treatment Period/ Vaccination Regimen	Use
Arm 1 Cohort 1 :rrcHL Cohort 2 rrPMBCL	Pembrolizumab (MK-3475)	25 mg/mL	400 mg	IV Infusion	Day 1, then Q6W up to 18 doses (approximately 2 years)	Test Product

Other current or former name(s) or alias(es) for study intervention(s) are as follows:
MK-3475.

Total Number of Intervention Groups/Arms	1 arm, 2 cohorts

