3 HYPOTHESES, OBJECTIVES, AND ENDPOINTS

Hypotheses are aligned with objectives in the Objectives and Endpoints table.

In male and female, programmed cell death 1 protein (PD-1) naïve, participants ≥ 18 years of age with either

- rrcHL who have failed to respond or relapsed after ≥ 1 line of multiagent therapy (can include brentuximab vedotin), or who have failed to achieve a complete response (CR) or relapsed after auto-stem cell transplantation (SCT), or are ineligible for auto-SCT,

OR

- rrPMBCL who have failed to respond or relapsed after ≥ 2 lines of therapy (at least 1 of the prior lines of therapy must contain a rituximab-based regimen), or who have failed to achieve a CR or relapsed after auto-SCT, or are ineligible for auto-SCT:

Primary Objective	Primary Endpoint
To evaluate objective response rate (ORR), by cohort, rrcHL and rrPMBCL, as assessed by the investigator according to Lugano classification criteria [Cheson, B. D., et al 2014] in individuals treated with pembrolizumab Q6W.	Participants with complete response (CR) or partial response (PR).
Secondary Objectives	Secondary Endpoints
To evaluate objective response rate (ORR), by cohort, rrcHL and rrPMBCL, as assessed by blinded independent central review (BICR) according to Lugano classification criteria [Cheson, B. D., et al 2014] in individuals treated with pembrolizumab Q6W.	Participants with complete response CR or PR.
To evaluate duration of response (DOR), by cohort, rrcHL and rrPMBCL, as assessed by the investigator according to Lugano classification criteria [Cheson, B. D., et al 2014] in individuals treated with pembrolizumab Q6W.	The time from first documented evidence of CR or PR until disease progression or death due to any cause, whichever occurs first.

To evaluate duration of response (DOR), by cohort, rrcHL and rrPMBCL, as assessed by BICR according to Lugano classification criteria [Cheson, B. D., et al 2014] in individuals treated with pembrolizumab Q6W.	The time from first documented evidence of CR or PR until disease progression or death due to any cause, whichever occurs first.
To evaluate the pharmacokinetic (PK) profile, immunogenicity of pembrolizumab 400 mg Q6W.	-PK parameters of pembrolizumab including AUC, C _{max} and C _{min} . -Antidrug antibody levels.
To evaluate the safety and tolerability of pembrolizumab Q6W.	-Adverse Events (AEs). -Discontinuations due to AEs.
Tertiary/Exploratory Objectives	Tertiary/Exploratory Endpoints
CCI	[REDACTED]

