4 STUDY DESIGN

4.1 Overall Design

This is a Phase 2, nonrandomized, multisite, open-label study of the efficacy and safety of IV pembrolizumab 400 mg Q6W in adult participants with rrCHL or rrPMBCL. Participants should be PD-1 naïve.

Participants with rrCHL (Cohort 1) must have failed to respond or relapsed after at least 1 line of multiagent therapy (chemotherapy with or without brentuximab vedotin), or have failed to achieve CR or relapsed after an auto-SCT, or are ineligible for auto-SCT.

Participants with rrPMBCL (Cohort 2) must have failed to respond or relapsed after ≥ 2 lines of prior therapy, or failed to achieve a CR or relapsed after auto-SCT or are ineligible for auto-SCT. At least 1 of the prior lines of therapy must contain a rituximab-based regimen. Participants with rrPMBCL must not require urgent cytoreductive therapy.

The study design is summarized in [Figure 1](#). The planned objectives and endpoints are detailed in Section 3.

After Screening, approximately 60 participants will receive pembrolizumab 400 mg fixed dose administered Q6W for up to 18 cycles (approximately 2 years) until documented disease progression per investigator assessment according to Lugano classification or the participant meets 1 of the discontinuation criteria (Section 7.1).

Disease will be assessed every 12 weeks using the Lugano response criteria [Cheson, B. D., et al 2014] per investigator assessment.

Participants who discontinue treatment for reasons other than disease progression will have posttreatment follow-up for disease status until disease progression, initiating a non-study cancer treatment, withdrawing consent, death, or becoming lost to follow-up. All participants will be followed for OS until death, withdrawal of consent, the end of the study, or becoming lost to follow-up, whichever comes first.

AEs will be monitored throughout the study and graded in severity according to the guidelines outlined in the NCI CTCAE 5.0. After the end-of-treatment, each participant will be followed for AE monitoring (see Section 8.4). Participants who undergo allogeneic SCT within 2 years after their last dose of study treatment will be followed for ECIs for up to 18 months post-transplant. This additional follow-up for participants undergoing an allogeneic SCT within 2 years after their last treatment is necessary to provide data for a post-marketing requirement from the FDA.

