6.3 Measures to Minimize Bias: Randomization and Blinding

6.3.1 Intervention Assignment

Enrollment into Cohorts 1 and 2 are of equal priority. All participants will receive 400 mg IV pembrolizumab Q6W.

Intervention allocation will occur centrally using an IRT system. There are 2 cohorts of participants and 1 study intervention arm.

Participants in this study will be allocated by nonrandom assignment.

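### Does it matter that Section 9.1 points to Section 3 for the rrPMBCL population, when Section 3 is broader than inclusion criterion 4?

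*Combined protocol and SAP*

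**What the plan says.** The Treatment Assignment row in Section 9.1 has two consecutive sentences that use different sources. The first gives the entry rule: "Participants meeting inclusion/exclusion criteria will be allocated to one of the 2 cohorts". The second gives a pointer: "The population of each cohort, rrCHL and rrPMBCL, is defined in Section 3".

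For rrPMBCL, the relevant texts are these.

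- **Section 3** (repeated at the start of the Section 1.1 synopsis) lists three alternatives. The first is failure or relapse after at least two lines, with the rituximab condition in brackets. The other two follow: "or who have failed to achieve a CR or relapsed after auto-SCT, or are ineligible for auto-SCT".
- **The synopsis population row** gives the same three alternatives and does not mention rituximab: "lines of therapy, or failed to achieve a CR or relapsed after auto-SCT, or are ineligible for auto-SCT".
- **Section 4.1** gives the same three alternatives and then puts rituximab in a separate sentence: "or are ineligible for auto-SCT. At least 1 of the prior lines of therapy must contain a rituximab-based regimen".
- **Section 5.1, criterion 4** has two routes. One is relapse after auto-SCT, or no CR or PR within 60 days of it. The other is auto-SCT ineligibility together with at least two prior lines and failure or relapse after the last one. The rituximab condition sits inside this second route.

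Section 5 forbids waivers of the entry criteria. Section 9.5.1 defines the all-participants-as-treated (APaT) set by allocation and at least one dose.

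**The concern.** This is a single-arm study that estimates and does not test, and its main result is an ORR for each cohort. With no comparator, a reader must know who could enter the cohort in order to interpret the estimate. If the SAP names one section as the definition while sites enrol under another, a report that follows the SAP could describe the wrong population.

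For rrPMBCL the two sections do differ. Read literally, Section 3 covers patients whom criterion 4 turns away. Section 4.1 can be read as turning away patients whom criterion 4 accepts, namely those who failed auto-SCT and never had rituximab. Section 9.9 expects low rrPMBCL enrolment, so each participant carries weight in that estimate. If the analysis set depended on which section was used, the denominator would be ambiguous.

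**Working it through.** The plan gives no figure to reproduce here. The check is whether the three definitions admit the same people, and whether any analysis step uses the difference.

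**Step 1: code the definitions.** Restrict to patients who meet the relapsed or refractory footnotes in Section 5.1. With those footnotes applied, the difference between CR in Section 3 and CR or PR in criterion 4 disappears. Then:

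- Section 3 = (at least 2 lines and rituximab) or post-auto-SCT or ineligible
- Section 4.1, rituximab read as cohort-wide = (at least 2 lines or post-auto-SCT or ineligible) and rituximab
- Criterion 4 = post-auto-SCT or (ineligible and at least 2 lines and rituximab)

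**Step 2: enumerate.** There are 3 transplant states × 2 line counts × 2 rituximab states × 2 outcomes (relapsed, refractory) = 24 profiles. The outcome does not alter the result, so 12 combinations suffice, each counting twice.

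| Transplant status | Lines | Rituximab | Combinations | Section 3 | Section 4.1 | Criterion 4 |
|---|---|---|---|---|---|---|
| Post-auto-SCT | 1 or ≥2 | yes | 2 | in | in | in |
| Post-auto-SCT | 1 or ≥2 | no | 2 | in | out | in |
| Ineligible | ≥2 | yes | 1 | in | in | in |
| Ineligible | ≥2 | no | 1 | in | out | out |
| Ineligible | 1 | yes | 1 | in | in | out |
| Ineligible | 1 | no | 1 | in | out | out |
| Eligible, untransplanted | ≥2 | yes | 1 | in | in | out |
| Eligible, untransplanted | ≥2 | no | 1 | out | out | out |
| Eligible, untransplanted | 1 | yes or no | 2 | out | out | out |

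- Section 3: 9 × 2 = 18 profiles
- Section 4.1: 5 × 2 = 10
- Criterion 4: 5 × 2 = 10
- In Section 3 but not criterion 4: 4 × 2 = 8
- In criterion 4 but not Section 3: 0
- In criterion 4 but not Section 4.1: 2 × 2 = 4
- In Section 4.1 but not criterion 4: 2 × 2 = 4

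These count logical profiles, not patients. The documents give no frequencies.

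**Step 3: vary the two uncertain readings.** The visible text does not define auto-SCT ineligibility. If sites class every untransplanted patient after two or more lines as ineligible, the eligible row with at least two lines and rituximab merges into a row that criterion 4 admits. The one-line ineligible rows and the ineligible row without rituximab still differ. If the rituximab sentence in Section 4.1 refers back only to the route with at least two lines, Section 4.1 equals Section 3 (18 profiles) and excludes nobody whom criterion 4 admits.

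**Step 4: trace the effect on the estimate.** Let n be the rrPMBCL participants allocated and dosed, and x the responders. The ORR is x/n with a Clopper-Pearson interval (Section 9.6.1.1). Section 9.5.1 sets n without reference to Section 3. Suppose an analyst did apply Section 3 as a filter. Criterion 4 lies wholly inside Section 3, so the filter removes 0 of the n properly enrolled participants, and x, n and the interval stay the same. Section 9 does not use Section 4.1 to define a population.

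**Step 5: check cohort membership.** The synopsis says "participants will be allocated into 2 cohorts based on baseline disease as described in Section 6.3.1". Section 6.3.1 adds only the mechanics, but the basis, baseline disease, is stated in the synopsis itself. None of the differences above moves a participant from one cohort to the other.

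**The case for a change.** The strongest case for acting is that Section 9.1 claims to say where the population is defined, not merely summarised, and names a section that does not match the entry rule. A summary may drop detail. Section 4.1, however, uses mandatory wording and, on the cohort-wide reading, contradicts criterion 4 over post-auto-SCT patients without rituximab. The study answers an FDA post-marketing requirement, and correcting the text would be cheap.

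Much of this stands as a matter of drafting. The texts conflict, they are fully visible, and criterion 4 does not refer to the country-specific appendix, so redaction does not explain the conflict. What does not stand is the step from there to the analysis. The sentence just before the pointer already gives the operative rule. Section 9.1 describes itself as a summary of Sections 9.2 to 9.12, and the analysis population there makes no use of Section 3. The contradiction in Section 4.1 depends on one of two tenable readings, and Section 4.1 is an overview, not the eligibility list. The risk of a report that overstates the population is hypothetical, and Section 9.6.3 already commits to summarising prior therapies, which will show who was actually enrolled.

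**Conclusion.** The inconsistency is genuine, of the lowest severity, and editorial. For rrPMBCL, Section 3 is over-broad relative to criterion 4 but excludes nobody whom criterion 4 admits. The change in ORR, denominator and confidence interval is zero. The only thing affected is how the rrPMBCL population is described, and an analyst writing the report would naturally take that from the Section 5.1 criteria and the prior-therapy tables.

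This conclusion assumes that sites enrol under Section 5.1, as Sections 5 and 9.1 require, and that the relapsed and refractory footnotes carry over to Section 3. If a site screened by Section 4.1 instead, on its cohort-wide reading, a patient might be refused. That would affect recruitment and not the analysis of those enrolled, and the documents give no figure for how often it could happen. The rrcHL wording was not pursued, because criterion 5 refers to an appendix that is not in the public text. This review takes no view on which eligibility wording is right; aligning the sections is a drafting matter for the sponsor.

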9.2 Responsibility for Analyses/In-house Blinding

The statistical analysis of the data obtained from this study will be the responsibility of the Clinical Biostatistics department of the Sponsor.

This study is being conducted as a non-randomized, open-label study; ie, participants, investigators, and Sponsor personnel will be aware of participant treatment assignments after each participant is enrolled and treatment is assigned.

9.3 Hypotheses/Estimation

Objectives of the study are stated in Section 3.

9.4 Analysis Endpoints

Efficacy, safety, and PK endpoints that will be evaluated are listed below, followed by the descriptions of the derivations of selected endpoints.

9.4.1 Efficacy Endpoints

Primary

- Objective Response Rate

The ORR is defined as the proportion of participants who achieve a CR or PR per Lugano classification as assessed by investigator.

Secondary

- Objective Response Rate

The ORR is defined as the proportion of participants who achieve a CR or PR per Lugano classification as assessed by BICR.

- Duration of Response

For participants who demonstrate CR or PR, DOR is defined as the time from the first documented evidence of CR or PR until disease progression or death due to any cause, whichever occurs first. DOR will be created, separately, for investigator and BICR assessments.

CCI [REDACTED]

[REDACTED]

[REDACTED]

9.4.2 Safety Endpoints

The safety endpoints include AEs, SAEs, and study treatment discontinuation due to AEs. In addition, safety and tolerability will be assessed by clinical review of all relevant parameters including AEs, laboratory tests, vital signs, and ECGs. A description of safety measures is provided in Section 8.3 and 8.4.

9.4.3 Pharmacokinetic Endpoints

PK and ADA analyses will be reported in separate memos that will be attached to the CSR as an appendix. PK and ADA data will be analyzed after all participants complete Cycle 5. PK parameters, such as AUC, C_{max} , and C_{min} as well as incidence of ADA, will be summarized (see Sections 4.2.1.3, 4.2.1.4, and 8.6 for additional details).

9.5 Analysis Populations

9.5.1 Efficacy Analysis Population

The APaT population will be used for the primary analysis of efficacy data in this study. The APaT population consists of all allocated participants who received at least 1 dose of study treatment.

9.5.2 Safety Analysis Population

The APaT population will be used for the analysis of safety data in this study. The APaT population consists of all allocated subjects who received at least 1 dose of study treatment.

At least 1 laboratory, vital sign, or ECG measurement obtained after at least 1 dose of study treatment is required for inclusion in the analysis of each specific parameter. To assess change from baseline, a baseline measurement is also required.

